2.4.3.3 Dose and administration

Patients with body surface area (BSA) $> 1.5 \text{ m}^2$ will receive 20 mg/kg (actual body weight) PO or IV twice daily (maximum 1 g per dose). Intravenous doses are infused over a two-hour period.

For patients from 1.25 to 1.5 m^2 , administer 750 mg IV or as capsules PO twice daily.

For patients $< 1.5 \text{ m}^2$ receiving suspension (not capsules), MMF as oral suspension can be given at a dose of 600 mg/ m^2 PO twice daily (maximum 1 g twice daily).

If patients with GI GVHD are assigned to MMF, and they cannot tolerate oral fluids greater than 500 mL per day ($200 \text{ mL}/\text{m}^2$), then MMF should be administered intravenously for the first 3-7 days of therapy and converted to oral MMF as soon as possible after the initial 3 days of therapy if oral medications and this limited fluid intake are tolerated.

A study of MMF absorption and pharmacokinetics is part of the trial (Appendix C-5) but levels will not be used for dose modification.

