2.4.3.5 Guidelines for MMF dose adjustment

If any toxicity is judged on clinical grounds related to MMF administration, dose adjustment can occur as follows:

Gastrointestinal (GI) Toxicity: If GI toxicity requires medication for control of persistent vomiting or diarrhea (not related to GVHD), a dose reduction to 50% can be instituted or, if symptoms persist and are severe (Grade 3 or 4), the drug can be stopped. If GI toxicity does not resolve within 48-72 hours of stopping MMF, then this toxicity is not likely related to MMF and the drug should be restarted. The study site principal investigator should be consulted before discontinuing MMF for GI toxicity.

Myelosuppression: If the ANC is less than 1000/ μ L, MMF dosing should be reduced by 50%. If the ANC is less than 500/ μ L, the drug should be discontinued until neutrophil recovery occurs. Use of filgrastim and/or discontinuation of other myelosuppressive agents is allowed.

Guidelines for Renal Insufficiency: As free MPA exposure has not been directly correlated with renal dysfunction, MMF dosing should not be modified unless renal failure requiring dialysis is required. If dialysis is needed, MMF can be reduced to 25% - 50% of the starting dose.

Hepatic Dysfunction: No adjustments of MMF are required for liver dysfunction.

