The frozen skin samples will be batch-shipped quarterly on dry ice by overnight delivery to the laboratory of [name] at Loyola University of Chicago.

C-5. MYCOPHENOLATE PHARMACOKINETICS

Added sampling for MMF and metabolite concentration and clearance calculations will be conducted during weeks 1 (between Days 3-7) and week 2 (Days 10-14) for patients assigned to receive MMF. Sampling will be done at hour 0 (pre-dose), 1, 2 and 6 hours for patients receiving oral MMF and hour 0, 2, 4 and 6 hours for patients receiving IV (infusion over 2 hours) MMF.

Pharmacokinetic Methods:

Pharmacokinetics will be studied twice in each subject following the initiation of MMF and corticosteroids for the treatment of acute GVHD. Patients will be sampled at steady-state once in week 1 (between Days 3-7) and again in week 2 (between Days 10-14) of MMF treatment. Steady-state is defined as a minimum of 4 identical mycophenolate mofetil doses given 12 hours apart.

Blood samples will be obtained at times 0, 1, 2, 6 hours following the administration of the oral dose and at 0, 2, 4 and 6 hours after the start of the IV infusion if receiving IV MMF. Intravenous MMF must be administered at a constant rate over 2 hours. Five mL of blood will be drawn at each time point from an existing central venous catheter or a temporary peripheral venous catheter.

Serum albumin, serum creatinine and total bilirubin will be measured, height and weight, medical history, and a detailed list of concomitant medications will be obtained on the day of each pharmacokinetic sampling. The pharmacokinetic form (included in the shipping box) will be completed for each pharmacokinetic sampling period.

MPA and MPAG Plasma Sample Processing and Storage:

Blood samples (5 mL) will be collected in a 10 mL purple top tube containing EDTA anticoagulant and placed on wet ice. Optimally, samples will be processed within 30 minutes of withdrawal, however samples are stable for up to 4 hours at room temperature or 8 hours if refrigerated at 1-4 degrees C. Samples should be prepared by centrifugation at 3400 rpm x 10 minutes, plasma removed and divided equally between two 5 mL screw top plastic tubes and then frozen at -20 degrees C. Samples should be stored frozen at -20 degrees C and then batch shipped after the completion of week 1 and 2 for each patient, frozen on dry ice in the provided shipping container to the University of Minnesota.

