Total MPA and MPAG, and unbound MPA will be measured with high-pressure liquid chromatography methods. Total MPA and MPAG concentrations are simultaneously measured. Unbound MPA concentrations are measured separately. The total MPA standard curve is prepared over the concentrations of 0.01 to 10 mcg/mL. MPAG standard curve is 1-100

mcg/mL. The unbound MPA standard curve is prepared over the concentrations of 0.0025 to 0.1 mcg/mL. Inter and intraday coefficients of variation are < 10% for both assays.

Data Analysis:

Exposure measures will be determined from four blood samples from which a 12-hour AUC will be calculated using the limited sampling model developed from data in a previous pharmacokinetic trial [40]. The primary exposure measures of interest are total and unbound MPA area under the curve (AUC), total and unbound MPA Cmax and Cmin, and free fraction. For each patient, an AUC will be calculated for each sampling period and will be used to investigate the interpatient variability, as measured by standard statistics such as standard deviation and coefficient of variation (CV). Graphs and correlations will be used to examine the distribution of values and bivariate relationships. The relationships between exposure measures and individual characteristics (age, gender, diagnosis, serum albumin, renal and hepatic function, site and grade of GVHD, height, weight, BSA) will be examined in order to identify potentially important variables that determine exposure. Intrapatient variability will be expressed by comparing the change in total exposure measures between the two sampling times. Clinical covariates (serum creatinine and albumin, total bilirubin, grade and site of GVHD at time of sampling) will be assessed for their relationship to changes in pharmacokinetic parameters. Exploratory analyses will be conducted to evaluate the relationship between acute GVHD resolution and MPA exposure.

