Cytokine Gene Polymorphism	3 mL peripheral blood sample (ACD-A anticoagulant yellow top tube or EDTA purple top tube) aliquoted into two 1.8 mL cryovials. Buccal Swab allowed to dry at room temperature and transferred into a 1.8 mL cryovial.	Frozen at -20°C	Pre-transplant (if blood available) and Day 0. Buccal Swab if pre-transplant blood not available	Shipped quarterly frozen on dry ice in a provided shipping container, FedEx priority overnight to the BMT CTN NIH sample repository	[name] Laboratory, Fred Hutchinson Cancer Research Center
Skin Biopsy	Two 4 mm punch biopsies, one biopsy in buffered formalin for routine histopathology. The second snap frozen in liquid nitrogen for research studies.	Second biopsy frozen at -80°C	Day 0 and Day 28	Shipped quarterly on dry ice to Loyola University	[name], Loyola University
Pharmacokinetics (Patients assigned to MMF arm only)	5 mL of peripheral blood sample (10 mL purple top tube containing EDTA anticoagulant) will be drawn at each timepoint, and medical information recorded. Sample placed on wet ice, then centrifuge for 10 minutes at 3400 RPM within 30 minutes of collection ² . Remove plasma and divide equally between two 5 mL plastic tubes.	Frozen at -20°C	Week 1 and Week 2 (Sampling will be done at 0, 1, 2, and 6 hours)	Shipped after completion of week 1 and week 2 on dry ice to University of Minnesota	[name], University of Minnesota

Note:

²Optimally, samples will be processed within 30 minutes of collection; however, samples are stable for up to 4 hours at room temperature or 8 hours if refrigerated at 1-4°C.

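### The laboratory table gives IV mycophenolate patients the oral sampling times, and the Appendix C-5 analysis accounts for neither route nor dose

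*Combined protocol and SAP*

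**What the plan says.** **Sampling windows.** Appendix C-5: "Patients will be sampled at steady-state once in week 1 (between Days 3-7) and again in week 2 (between Days 10-14) of MMF treatment".

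**Sampling times.** C-5 specifies "hour 0, 2, 4 and 6 hours for patients receiving IV (infusion over 2 hours) MMF" and 0, 1, 2 and 6 hours for oral MMF. It repeats this under Pharmacokinetic Methods, and the post-randomization list in Section 4.2.2 agrees. The pharmacokinetics row of the Schedule of Laboratory Evaluations, which covers everyone on the MMF arm, says only "Sampling will be done at 0, 1, 2, and 6 hours".

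**Route.** Section 2.4.3.3 sets the condition for starting IV: "If patients with GI GVHD are assigned to MMF, and they cannot tolerate oral fluids greater than 500 mL per day". In that case, "then MMF should be administered intravenously for the first 3-7 days of therapy and converted to oral MMF as soon as possible" once the initial 3 days are past, provided oral intake is tolerated.

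**Dose.** Section 2.4.3.3 gives 20 mg/kg with a 1 g ceiling above 1.5 m², 750 mg (IV or capsules) from 1.25 to 1.5 m², and 600 mg/m² for suspension below 1.5 m². For a neutrophil count under 1000/μL, Section 2.4.3.5 says that "MMF dosing should be reduced by 50" percent. It also allows halving for GI toxicity.

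**Analysis.** AUC comes from four samples through a limited sampling model built on an earlier trial. Determinants of exposure are sought among "age, gender, diagnosis, serum albumin, renal and hepatic function, site and grade of GVHD, height, weight, BSA". For within-patient variation, "Intrapatient variability will be expressed by comparing the change in total exposure measures between the two sampling times". Changes in pharmacokinetic parameters are then related to creatinine, albumin, bilirubin, and GVHD grade and site. Neither list contains route or dose, and no dose normalization is stated.

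**The concern.** There are two separate problems. The first concerns data collection: the table a site is likely to work from disagrees with the text, and a sample not drawn cannot be recovered.

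The second concerns analysis. For some patients the interval between the two samplings is also the interval in which route changes, and the patients concerned are defined partly by GVHD site, which is a listed covariate. If oral exposure is lower than IV exposure, the route switch appears as within-patient instability. GI involvement could then look like a cause of higher week 1 exposure, which could mask a genuine absorption defect. Section 2.4.3.3 describes this substudy as one of absorption, so route bears directly on its subject. Dose raises the same difficulty: under the 1 g ceiling, weight partly stands in for dose per kg.

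**Working it through.** The pharmacokinetic plan states no sample size, precision target or CV, so there is no figure to reproduce. The check compares the texts and then gives a bounded illustration.

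**1. Sampling times for an IV patient**

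| Source | Hours from start of 2-hour infusion |
|---|---|
| Section 4.2.2 | 0, 2, 4, 6 |
| Appendix C-5 (stated twice) | 0, 2, 4, 6 |
| Schedule of Laboratory Evaluations | 0, 1, 2, 6 |

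Under the table, the 1-hour draw falls mid-infusion and nothing is drawn between the end of infusion (2 h) and 6 h. Whether the limited sampling model could use those times for an IV patient is not stated. This conflict needs no assumption.

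**2. Can route differ between samplings?** Yes. A patient kept on IV through Day 7 has an IV profile in the Day 3-7 window and, once converted, an oral one on Days 10-14. Not every IV starter does. The steady-state rule (four identical doses 12 hours apart) can be met in about two days, so a patient converted after Day 3 can have an oral profile within the first window. Another may remain on IV in week 2.

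**3. Can dose differ?**
- Between patients: min(1000, 20 × weight)/weight gives 20 mg/kg at 50 kg, 1000/80 = 12.5 at 80 kg, and 1000/100 = 10 at 100 kg.
- Within a patient, at conversion: at 1.4 m², IV is 750 mg and suspension is 600 × 1.4 = 840 mg, which is 12% more.
- Within a patient, after a 50% reduction: if exposure is proportional to dose (an assumption), AUC halves, a log change of ln 0.5 = −0.69.

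The steady-state rule makes doses equal before each profile, not across the two.

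**4. Size of the route effect.** The documents give none of these inputs, so all are assumed: oral/IV exposure ratio F from 0.60 to 0.95, share f of sampled patients going from IV to oral from 10% to 50%, and true within-patient CV from 20% to 40%. Everyone else is same-route, and dose is unchanged. On the log scale:

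- s² = ln(1 + CV²)
- Var(week 2 − week 1) = 2s² + f(1 − f)(ln F)²
- mean log change = f ln F
- apparent within-patient CV = √(exp(Var/2) − 1)

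Example with F = 0.60, f = 50%, CV = 20%: s² = ln 1.04 = 0.0392, and the switch term is 0.25 × (−0.511)² = 0.0652. Var = 0.0784 + 0.0652 = 0.1437 before rounding. Apparent CV = √(exp(0.0718) − 1) = 27.3%. The switch supplies 0.0652/0.1437 = 45% of the variance, and the geometric mean change is exp(0.5 × −0.511) − 1 = −22.5%.

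Apparent CV for f = 10% / 25% / 50%:

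| F | True CV 20% | True CV 30% | True CV 40% |
|---|---|---|---|
| 0.60 | 22.9 / 25.6 / 27.3 | 32.1 / 34.2 / 35.5 | 41.7 / 43.4 / 44.5 |
| 0.80 | 20.6 / 21.2 / 21.6 | 30.4 / 30.8 / 31.1 | 40.3 / 40.7 / 40.9 |
| 0.95 | 20.0 / 20.1 / 20.1 | 30.0 / 30.0 / 30.1 | 40.0 / 40.0 / 40.0 |

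C-5 does not say how the change is to be summarized. If the mean shift were counted as variability (root mean square of the change), the worked example would give 33.2% instead of 27.3%.

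**5. Apparent effect of GVHD site.** At equal clearance and dose, an IV profile exceeds an oral one by 1/F: 1.67, 1.25 or 1.05 times for F = 0.60, 0.80 or 0.95. If only half of the GI patients are on IV in week 1 (assumed), the geometric mean ratio for GI patients against others is F^(−0.5): 1.29, 1.12 or 1.03.

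**The case against.** A reader might infer that the plan ignores route altogether. It does not. Section 4.2.2 and C-5 set times by route, C-5 requires a constant 2-hour infusion, and it gives IV-specific instructions on pumps, flushing and choice of lumen. The gap in the text is confined to the analysis.

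Nor is dose wholly absent. C-5 opens by mentioning clearance calculations, which need dose, and weight and BSA, which set the starting dose, are listed covariates. A pharmacokinetic form is completed at each sampling, though its contents are not shown. This stands in part: clearance is not among the primary measures listed in Data Analysis, and weight and BSA cannot reflect a later reduction.

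A reader might also infer that all GI patients switch route, so that misattribution is certain. The documents do not support that. Only those below the oral-fluid threshold start IV, and some of them will be on the same route at both samplings. The number is not given.

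Finally, one might conclude that the exposure-response analysis is invalid. The AUC a patient actually reached is a legitimate exposure whatever the route. The difficulty there is confounding by GVHD site and grade, and replacing the AUC with a route- and dose-adjusted value would remove the variation under study.

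**Conclusion.** Both parts hold, within limits. The sampling-time conflict is plain on the page and, if the table is followed, costs IV patients a sample that C-5 and Section 4.2.2 require. The analysis as written cannot separate a change of route or dose from intrapatient variability, and it can credit either to GVHD site or weight.

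This is a risk, not a certain result. Over the assumed ranges the switch contributes between almost nothing (at most about 1% of the variance of the change at F = 0.95) and 45% (F = 0.60, half switching, true CV 20%). Whether the limited sampling model covers both routes cannot be judged from the documents.

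The consequences stay within a one-arm ancillary study (Section 5.3 targets about 45 patients per arm) whose response analysis is labeled exploratory. Levels do not guide dosing (Section 2.4.3.3). A reader should not infer any effect on the Day 28 CR endpoint, the stopping rules or the selection of agents; none of these uses the pharmacokinetic data.

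**What to change.** 1. In the Schedule of Laboratory Evaluations, print both sets of times (oral 0, 1, 2, 6 h; IV 0, 2, 4, 6 h) so that it matches Section 4.2.2 and C-5. Do this before sampling starts.
2. Ensure that the existing pharmacokinetic form captures route and actual dose at each sampling.
3. In C-5 Data Analysis, state the route or routes for which the limited sampling model applies.
4. When examining determinants of exposure, include route and either dose or dose-normalized exposure.
5. Report intrapatient variability from same-route, same-dose pairs, and IV-to-oral pairs separately. State the summary measure.
6. For the exploratory relation with GVHD resolution, keep the achieved AUC and adjust for route, dose, and GVHD site and grade.

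The cost is one table cell and a few sentences in C-5. Route must already be known to choose sampling times and dose is known when given, so no extra sample is needed and no clinical rule changes. The drawback is that fewer pairs enter the intrapatient estimate, which will be less precise.

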APPENDIX D
HUMAN SUBJECTS

APPENDIX D

HUMAN SUBJECTS

Subject consent: Candidates for the study will be identified as described in Chapter 4 of the protocol. The Principal Investigator or his/her designee at each transplant center will contact the candidates and enroll them onto the study. The study coordinator at each center will provide the patient with information about the purpose of the study and obtain consent. The Network will provide a template of the consent form to each center. Each center will customize the template according to their local requirements and submit it for review by the local Internal Review Board (IRB). The DCC will verify the adequacy of the consent forms. Each center must provide evidence of IRB approval.

Confidentiality: Confidentiality will be maintained by individual names being masked and assigned a patient identifier code. The code relaying the patient's identity with the ID code will be kept separately at the center. The ID code will be transmitted to the network.

Participation of women, children, minorities and other populations: Women, children and ethnic minorities will be included in this study.

Accrual will be monitored within each center with the expectation that the enrolled patient population is representative of the transplanted patient population at each center. Representation will be examined by comparing gender, race, ethnicity and age distributions. Accrual of minority patients will be expected to be in proportion to the number of minority patients transplanted at each center. The DCC and NHLBI will discuss enrollment anomalies with the centers.
